 - >3 x ULN accompanied by signs or symptoms consistent with hepatic injury [eg, new onset elevated prothrombin time/international normalized ratio (PT/INR)];
 - Two sequential AST or ALT elevations >5 x ULN, regardless of total bilirubin or accompanying signs or symptoms.

NOTE: See also [Appendix 6](#) for potential cases of drug-induced liver injury.

Potential Cases of Acute Kidney Injury

Abnormal values in serum creatinine (SCr) concurrent with presence or absence of increase in blood urea nitrogen (BUN) that meet the criteria below, in the absence of other causes of kidney injury, are considered potential cases of acute kidney injury and should be considered important medical events.

An increase of ≥ 0.3 mg/dL (or ≥ 26.5 μ mol/L) in SCr level relative to the participant's own baseline measurement should trigger another assessment of SCr as soon as practically feasible, preferably within 48 hours from awareness.

If the second assessment (after the first observations of ≥ 0.3 mg/dL [or ≥ 26.5 μ mol/L] in SCr relative to the participant's own baseline measurement) is ≥ 0.4 mg/dL (or ≥ 35.4 μ mol/L), the participant should be discontinued from the study and adequate, immediate, supportive measures taken to correct apparent acute kidney injury.

Participants should return to the investigator site and be evaluated as soon as possible, preferably within 48 hours from awareness of the second assessment confirming abnormal SCr result. This evaluation should include laboratory tests, detailed history, and physical assessment. In addition to repeating SCr, laboratory tests should include serum BUN, serum creatine kinase, and serum electrolytes (including at a minimum potassium, sodium, phosphate/phosphorus, and calcium), in addition to urinary dipstick, urine microscopic

examination, and urinary indices. All cases confirmed on repeat testing as meeting the laboratory criteria for acute kidney injury, with no other cause(s) of laboratory abnormalities identified, should be considered potential cases of drug-induced kidney injury irrespective of availability of all the results of the investigations performed to determine etiology of the abnormal SCr. If ≥ 2 healthy participants at a given dose level are noted to have 2 consecutive SCr results of ≥ 0.3 mg/dL (or ≥ 26.5 μ mol/L), an assessment of whether the finding may be considered an adverse drug reaction should be undertaken.

Prohibited Medications

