10.3.2. Definition of SAE

If an event is not an AE per definition above, then it cannot be an SAE even if serious conditions are met (eg, hospitalization for signs/symptoms of the disease under study, death due to progression of disease).

An SAE is defined as any untoward medical occurrence that, at any dose:

a. Results in death

b. Is life-threatening

The term “life-threatening” in the definition of “serious” refers to an event in which the participant was at risk of death at the time of the event. It does not refer to an event that hypothetically might have caused death if it were more severe.

c. Requires inpatient hospitalization or prolongation of existing hospitalization

In general, hospitalization signifies that the participant has been detained (usually involving at least an overnight stay) at the hospital or emergency ward for observation and/or treatment that would not have been appropriate in the physician's office or outpatient setting. Complications that occur during hospitalization are AEs. If a complication prolongs hospitalization or fulfills any other serious criteria, the event is serious. When in doubt as to whether “hospitalization” occurred or was necessary, the AE should be considered serious.

Hospitalization for elective treatment of a preexisting condition that did not worsen from baseline is not considered an AE.

d. Results in persistent disability/incapacity

- The term disability means a substantial disruption of a person's ability to conduct normal life functions.
- This definition is not intended to include experiences of relatively minor medical

significance such as uncomplicated headache, nausea, vomiting, diarrhea, influenza, and accidental trauma (eg, sprained ankle) which may interfere with or prevent everyday life functions but do not constitute a substantial disruption.

e. Is a congenital anomaly/birth defect

f. Other situations:

- Medical or scientific judgment should be exercised in deciding whether SAE reporting is appropriate in other situations such as important medical events that may not be immediately life-threatening or result in death or hospitalization but may jeopardize the participant or may require medical or surgical intervention to prevent one of the other outcomes listed in the above definition. These events should usually be considered serious.

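### Protocol 7.1 limits the dose-level creatinine prompt to healthy participants, a population this study does not define or enrol, and leaves the own-baseline reference off two creatinine thresholds (minor, wrong as written)

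*Protocol*

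**What the plan says.** All the wording at issue is in Protocol 7.1, under potential cases of acute kidney injury.

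- **First trigger.** A rise in serum creatinine (SCr) of ≥0.3 mg/dL (≥26.5 µmol/L) from the participant's "baseline measurement should trigger another assessment of SCr as soon as practically feasible". The baseline reference is explicit.
- **Second assessment.** The baseline reference sits in a parenthesis that describes the first observation. The parenthesis closes and the operative clause begins: "own baseline measurement) is" ≥0.4 mg/dL (≥35.4 µmol/L). If that is met, "the participant should be discontinued from the study and adequate, immediate, supportive measures taken to correct apparent acute kidney injury".
- **Follow-up.** The evaluation is timed from "awareness of the second assessment confirming abnormal SCr result". Cases confirmed on repeat testing with no other cause found "should be considered potential cases of drug-induced kidney injury".
- **Dose-level prompt.** If two or more "healthy participants at a given dose level are noted to have 2 consecutive SCr results of" ≥0.3 mg/dL (≥26.5 µmol/L), the study is to assess whether the finding is an adverse drug reaction. No baseline is mentioned.

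On population, Protocol 4.1 and 5.1 provide for participants with T2DM on metformin (Parts A and C) and, optionally, non-diabetic obese participants (Part B). Protocol 5.2 also allows controlled chronic conditions such as hypertension. Apart from titles in the reference lists, the only other use of the word healthy for participants is in Protocol 2.2.4, which describes the earlier single-dose study.

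**The concern.** These are operative safety instructions in a study whose primary objective is safety and which is the first to give repeated doses to humans (Protocol 4.2.4.1). Two sentences say something other than what is meant.

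The prompt is the only creatinine-specific rule in 7.1 that looks across participants at a dose level. As worded, it leaves out the population for which the study is mainly designed.

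The repeat test exists to separate a transient rise from a confirmed one. If the 0.4 figure is read as a plain creatinine value, the repeat separates almost nobody, and a participant whose creatinine has recovered would be taken out of the study. That adds no drug exposure, but it costs data in cohorts of about 10.

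**Working it through.** **1. The plan's figures.** With the usual conversion of 88.4 µmol/L per mg/dL (not stated in the documents), 0.3 × 88.4 = 26.52 and 0.4 × 88.4 = 35.36. Both match the printed 26.5 and 35.4. The numbers are sound; only the words around them are in question.

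**2. Who the prompt covers.** Planned maximum from Protocol 4.1:

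| Part | Population | Cohorts × size | Participants |
|---|---|---|---|
| A | T2DM | 5 × 10 | 50 |
| B | Non-diabetic obese | 2 × 15 | 30 |
| C | T2DM | 2 × 10 | 20 |
| Total | | | 100 |

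T2DM participants number 50 + 20 = 70 of 100. None can be called healthy. The other 30, in Part B, are never called healthy in the protocol.

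**3. What 0.4 mg/dL means as an absolute value.** Protocol Appendix 2 gives the MDRD equation:

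eGFR = 175 × SCr^−1.154 × age^−0.203 × 0.742 [female] × 1.212 [black]

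eGFR (mL/min/1.73m²) at SCr = 0.4, over the eligible age range of 18 to 70:

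| Age | Male | Female | Male, with 1.212 | Female, with 1.212 |
|---|---|---|---|---|
| 18 | 280 | 208 | 340 | 252 |
| 50 | 228 | 169 | 276 | 205 |
| 70 | 213 | 158 | 258 | 191 |

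The range is 158 to 340. At SCr = 0.3 the same calculation gives 220 to 473.

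**4. Where baselines lie.** Exclusion criterion 22 requires eGFR of at least 60. Inverting the equation:

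SCr = (175 × age^−0.203 × factors / eGFR)^(1/1.154)

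| eGFR | Baseline SCr, ages 18 to 70, both sexes, without the 1.212 factor (mg/dL) |
|---|---|
| 60 | 0.92 to 1.52 |
| 120 | 0.51 to 0.83 |
| 150 (assumed upper end) | 0.42 to 0.69 |

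Values are higher with the 1.212 factor. All exceed 0.4, so over this range a repeat exactly at baseline meets the literal threshold.

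**5. Illustration with chosen values (not a rate).** Baseline 0.90, first value 1.25, repeat 0.90 mg/dL. The first rise is 1.25 − 0.90 = 0.35, so the repeat is triggered. The repeat shows a change of 0. The literal test (0.90 ≥ 0.4) is met; the intended test (rise ≥ 0.4) is not.

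**6. Both corrections are needed.** Deleting only the word healthy would let any two participants with ordinary creatinine trigger the prompt, since ordinary values exceed 0.3. Adding only the baseline reference would still leave T2DM participants outside it.

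**The case against.** The strongest reply is that the missing baseline reference is shorthand and not a wrong rule. The subsection opens by limiting itself to abnormal creatinine values, and 0.4 mg/dL is not an elevated creatinine. The parenthesis names own baseline just before the threshold and already uses a bare figure for a rise. The next paragraph treats the second test as confirmatory. On this view the MDRD figures only show why no site would apply the literal reading. This largely stands: intent can be recovered, and a reader who infers that participants will in practice be discontinued at normal creatinine goes further than the documents allow.

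On the word healthy, Part B participants without significant disease might loosely be called so. A reader might therefore infer too much in saying that the prompt applies to nobody. What the documents support is that it excludes all T2DM participants and that Part B is never described in those terms.

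Nor do the documents support the inference that a kidney signal would go unnoticed:

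- Cases meeting the criteria in 7.1 "are considered potential cases of acute kidney injury and should be considered important medical events". Of such events, Protocol 10.3.2 says: "These events should usually be considered serious". An SAE on active drug pauses dosing, and escalation can be halted for other findings (6.6.1).
- Clinically significant laboratory values are recorded as AEs and repeated (8.2.4), with causality assessed for each AE (10.3.3).
- Laboratory data are reviewed on an ongoing basis (9.4.2) and at escalation (Appendix 2).

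Some of these routes rest on judgement. It would also go too far to call the prompt redundant on the ground that the single-case route always acts first. The documents give no creatinine event rate, and which route acts more often depends on the rates assumed.

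**Conclusion.** The point holds as a minor wording error in two sentences. The clearer fault is the population restriction: at full enrolment, 70 of 100 participants are outside the prompt on any reading. The missing baseline reference is an error of expression whose intended meaning is evident from context, although the literal rule would be met by a repeat at baseline anywhere from eGFR 60 to the assumed upper end of 150.

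The practical effect is small. The prompt calls only for an assessment, and it adds something separate mainly for rises sustained at 0.3 to below 0.4 mg/dL, and only if a confirmed case is taken to need the 0.4 repeat. No endpoint, sample size or analysis is affected. The calculation rests on the protocol's own equation and entry limits; the upper eGFR of 150 and the conversion factor are the only outside inputs.

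**What to change.** Change two sentences in Protocol 7.1:

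- Discontinuation threshold: *is an increase of ≥0.4 mg/dL (≥35.4 µmol/L) relative to the participant's own baseline*.
- Dose-level prompt: *If ≥2 participants at a given dose level have 2 consecutive SCr increases of ≥0.3 mg/dL (≥26.5 µmol/L) relative to their own baseline*, with the word healthy deleted.

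The cost is a wording correction at the next amendment. Until then, a short written clarification to sites would serve.

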7.2. Participant Discontinuation/Withdrawal From the Study

A participant may withdraw from the study at any time at his/her own request or may be withdrawn at any time at the discretion of the investigator for safety, behavioral, compliance, or administrative reasons.

At the time of discontinuing from the study, if possible, an early discontinuation visit should be conducted. See the [Schedule of Activities](#) for assessments to be collected at the time of study discontinuation and follow-up and for any further evaluations that need to be completed.

The early discontinuation visit applies only to participants who are randomized and then are prematurely withdrawn from the study. Participants should be questioned regarding their reason for withdrawal.

The participant will be permanently discontinued both from the study intervention and from the study at that time.

If a participant withdraws from the study, he/she may request destruction of any remaining samples, but data already generated from the samples will continue to be available, and may be used to protect the integrity of existing analyses. The investigator must document any such requests in the site study records.

If the participant withdraws from the study and also withdraws consent (see below) for disclosure of future information, no further evaluations should be performed and no additional data should be collected. The sponsor may retain and continue to use any data collected before such withdrawal of consent. When a participant withdraws from the study because of an SAE, the SAE must be recorded on the CRF and reported on the Clinical Trial (CT) SAE Report.

Lack of completion of all or any of the withdrawal/early termination procedures will not be viewed as protocol deviations so long as the participant's safety was preserved.

Withdrawal of Consent:

Participants who request to discontinue receipt of study treatment will remain in the study and must continue to be followed for protocol-specified follow-up procedures. The only exception to this is when a participant specifically withdraws consent for any further contact with him or her or persons previously authorized by the participant to provide this information. Participants should notify the investigator in writing of the decision to withdraw consent from future follow-up, whenever possible. The withdrawal of consent should be explained in detail in the medical records by the investigator, as to whether the withdrawal is only from further receipt of investigational product or also from study procedures and/or posttreatment study follow-up, and entered on the appropriate CRF page. In the event that vital status (whether the participant is alive or dead) is being measured, publicly available information should be used to determine vital status only as appropriately directed in accordance with local law.

7.3. Lost to Follow up

A participant will be considered lost to follow-up if he or she repeatedly fails to return for scheduled visits and is unable to be contacted by the study site.

The following actions must be taken if a participant fails to return to the clinic for a required study visit:

- The site must attempt to contact the participant and reschedule the missed visit as soon as possible and counsel the participant on the importance of maintaining the assigned visit schedule and ascertain whether or not the participant wishes to and/or should continue in the study;
- Before a participant is deemed lost to follow-up, the investigator or designee must make every effort to regain contact with the participant (where possible, 3 telephone calls and, if necessary, a certified letter to the participant's last known mailing address or local equivalent methods). These contact attempts should be documented in the participant's medical record;
- Should the participant continue to be unreachable, he/she will be considered to have withdrawn from the study.

Discontinuation of specific sites or of the study as a whole is handled as part of [Appendix 1](#).

8. STUDY ASSESSMENTS AND PROCEDURES

Participants will be screened within 28 days prior to administration of the investigational product to confirm that they meet the study population criteria for the study. The investigator (or an appropriate delegate at the investigator site) must obtain a signed and dated ICD **before performing any study-specific procedures**. If the time between screening and dosing exceeds 28 days as a result of unexpected delays (eg, delayed drug shipment), then

participants do not require rescreening if the laboratory results obtained prior to first dose administration meet eligibility criteria.

A participant who qualified for this protocol but did not enroll from an earlier cohort/group may be used in a subsequent cohort/group without rescreening, provided laboratory results obtained prior to the first dose administration meet eligibility criteria for this study. [REDACTED]

Study procedures and their timing are summarized in the [Schedule of Activities](#). Protocol waivers or exemptions are not allowed.

Immediate safety concerns should be discussed with the sponsor immediately upon occurrence or awareness to determine if the participant should continue or discontinue study intervention.

Adherence to the study design requirements, including those specified in the [Schedule of Activities](#), is essential and required for study conduct.

All screening evaluations must be completed and reviewed to confirm that potential participants meet all eligibility criteria. The investigator will maintain a screening log to record details of all participants screened and to confirm eligibility or record reasons for screening failure, as applicable.

Every effort should be made to ensure that protocol-required tests and procedures are completed as described. However, it is anticipated that from time to time there may be circumstances outside the control of the investigator that may make it unfeasible to perform the test. In these cases, the investigator must take all steps necessary to ensure the safety and well-being of the participant. When a protocol-required test cannot be performed, the investigator will document the reason for the missed test and any corrective and preventive actions that he or she has taken to ensure that required processes are adhered to as soon as possible. The study team must be informed of these incidents in a timely manner.

All efforts will be made to conduct procedures at the exact nominal time relative to dosing. Procedures up to and including 10 hours after dose administration that are conducted within 10% of the nominal time (eg, within 6 minutes of a 60-minute sample) relative to dosing will not be captured as a protocol deviation, as long as the exact time of the procedure is noted on the source document and data collection tool (eg, CRF/DCT). Procedures scheduled more than 10 hours after dose administration that are conducted \leq 1 hour away from the nominal time relative to dosing will not be captured as a protocol deviation, as long as the exact time of the procedure is noted on the source document and data collection tool (eg, CRF/DCT).

When multiple procedures are scheduled at the same time point(s) relative to dosing, the following chronology of events should be adhered to, where possible:

- *ECGs*: obtain prior to vital sign measurements and as close as possible to the scheduled time, but prior to blood specimen collection (refer to [Section 8.2.3](#));
- *Vital Signs (BP and pulse rate)*: obtain as close as possible to the scheduled time, but prior to blood specimen collection (refer to [Section 8.2.2](#));
- *Weight*: obtain as close as possible to the scheduled time, but prior to eating and drinking and prior to dose administration, where applicable (refer to [Section 8.6.3](#));
- *Fasting blood samples*: after assessment of 12-lead ECG and vital signs but prior to dosing;
- *PK blood specimens*: obtain at the scheduled time (for 0H samples, collect before dosing and as close as possible to dosing time, where applicable);
- *Dosing*: must occur at the scheduled nominal time and following predose blood sample collection;
- *Breakfast*: provided for consumption following dosing, where applicable (see [Section 5.3.1](#)).

Note that if an IV catheter is placed for serial blood sample collections, ECGs and vital signs (pulse rate, BP) assessments should be either collected prior to the insertion of the catheter or sufficient rest period after catheter insertion introduced to minimize impact of catheter placement on these assessments.

For samples being collected and shipped, detailed collection, processing, storage, and shipment instructions and contact information will be provided to the investigator site prior to initiation of the study.

The total blood sampling volume for individual participants in **Part A** of this study is approximately 535 mL.

The total blood sampling volume for individual participants in **Part B** of this study is approximately 420 mL.

The total blood sampling volume for individual participants in **Part C** of this study is approximately 525 mL.

The actual collection times of blood sampling may change. Additional blood samples may be taken for safety assessments at times specified by Pfizer, provided the total volume taken during the study does not exceed 550 mL during any period of 60 consecutive days.

To prepare for study participation, participants will be instructed on the information in the [Lifestyle Considerations](#) and [Concomitant Therapy](#) sections of the protocol.

8.1. Efficacy Assessments

Not applicable.

8.2. Safety Assessments

Planned time points for all safety assessments are provided in the [Schedule of Activities](#). Unscheduled clinical laboratory measurements may be obtained at any time during the study to assess any perceived safety concerns.

8.2.1. Physical Examinations

A complete physical examination will include, at a minimum, head, ears, eyes, nose, throat/mouth, neck, skin, cardiovascular, respiratory, gastrointestinal, lymphatic, musculoskeletal, and neurological systems.

A brief physical examination will include, at a minimum, assessments of general appearance, the respiratory and cardiovascular systems, and participant-reported symptoms.

Physical examinations may be conducted by a physician, trained physician's assistant, or nurse practitioner as acceptable according to local regulation.

8.2.2. Vital Signs

Supine BP will be measured with the participant's arm supported at the level of the heart, and recorded to the nearest mm Hg after approximately 5 minutes of supine rest. The same arm (preferably the dominant arm) will be used throughout the study. Participants should be instructed not to speak during measurements.

When triplicate measurements are required (see [Schedule of Activities](#)), they will be obtained approximately 3 minutes (± 1 minute) apart; the average of the triplicate measurements on Day -1 will serve as each participant's time-controlled baseline value. The same properly sized and calibrated BP cuff will be used to measure BP each time. The use of an automated device for measuring BP and pulse rate is acceptable; however, when done manually, pulse rate will be measured in the brachial/radial artery for at least 30 seconds. When the timing of these measurements coincides with a blood collection, BP and pulse rate should be obtained prior to the nominal time of the blood collection.

Additional collection times, or changes to collection times, of BP and pulse rate will be permitted, as necessary, to ensure appropriate collection of safety data.

